Safety data from the Investigators Brochure on the OPERA I and II phase 3 trials comparing ocrelizumab to interferon β -1a on relapsing MS patients showed that IRRs were the most common adverse events experienced by patients treated with 600 mg of ocrelizumab.⁴ The percentage of patients experiencing IRRs was higher in the ocrelizumab group (relapsing forms of MS: 34.3%; primary progressive forms of MS 39.9%) compared with the interferon β -1a (active control) group who received placebo infusions (relapsing forms of MS: 9.7%; primary progressive forms of MS: 25.5%). The rate of IRRs was highest during the first infusion or Dose 1 (27.5% on Day 1; 4.71% on Day 15 of Dose 1) and decreased over time (13.7%; 9.6% and 7.8% following Dose 2, 3, and 4 respectively) for the ocrelizumab treated group. Comparatively, interferon β -1a users experienced 6.5% of IRRs on Day 1, 2.58% on Day 15, \leq 2.00% after doses 2, 3 and 4 respectively. The reported IRRs were primarily mild-to-moderate in severity (Grades 1 and 2). Serious IRRs occurred in 0.1% and 1.0% respectively of relapsing and progressive patients and treated with ocrelizumab.

Clinical data describing the efficacy and tolerability profile of rituximab and ocrelizumab has utilized populations with different prior treatment characteristics. In the phase 2 HERMES trials, a majority (78.5%) of rituximab patients had been **previously been treated** with a disease modifying therapy in the last 2 years.³ In contrast, the OPERA I and II phase 3 clinical trials, a majority of ocrelizumab

patients (72.9% in OPERA I and 73.8% in OPERA II) represented a **treatment naïve population**.⁴ Examining IRRs in patients who have switched from rituximab to ocrelizumab versus those continuing on rituximab will evaluate the magnitude of the IRRs and subsequent tolerability of ocrelizumab in a real world population of MS patients previously been exposed to rituximab.

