For patients who are switching to ocrelizumab, the first dose of ocrelizumab will be a split dose of 300 mg on day 1 and day 15 followed by 600 mg, six months later as approved by the FDA. The timing of 12 month dose may be delayed due to vagaries in the approval of biologics by third payors. Therefore, we will include data from patients at the T3 visit between the month 12 and 18 after starting ocrelizumab. Standard of care rituximab doses are 1000 mg given as first dose followed by 500mg (or 1000 mg if evidence of early B cell recovery) every 6 months thereafter. Study patients will be current patients of the RMMSC who meet the inclusion criteria and are currently receiving rituximab infusions from the University of Colorado Hospital's Outpatient Infusion Center. Analysis of IRRs will be conducted by the research team at RMMSC. Anti-drug antibody analysis will be conducted by two external vendors: PPD Bio A Laboratories, Richmond, VA will conduct the anti-drug antibodies assays for ocrelizumab, QPS Netherlands, Netherlands will conduct the anti-drug antibodies assays for rituximab using cryopreserved blood samples sent by the RMMSC research team as a single batch at the end of the study. Cytokine analysis will be conducted by personnel at the biobank repository at RMMSC. Study duration, including the recruitment (estimated to take 6 months), data analysis and manuscript development is anticipated to be 24 months.

The study design is represented in **Figure 1** below and described in further detail in section 4.5.1

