3.3 Outcome Measures

3.3.1. Primary Outcome Measure

Primary endpoint:

- a. Primary endpoint: The primary end point will be proportion of infusions with ≥ 1 IRR between the switching and comparator groups.
- b. Secondary IRR assessments:
 - a. We will also report the difference in the total number of IRRs after each infusion of ocrelizumab in the switching group compared to similar rituximab infusions in the comparator group.
 - b. The difference in proportion of patients with ≥ 1 IRR across any of their infusions between the switching and comparator groups
 - c. We will also compare the proportion of patients with an IRR following day 1 infusion versus the proportion of patients with an IRR at day 15 and month 6 infusions of ocrelizumab in the switching group.
 - d. The severity of IRRs will be assessed following each infusion of ocrelizumab in the switching and comparator group using the National Cancer Institute's Common Terminology for Adverse Events Scale.⁶ The frequency of each severity grade of IRR will be compared in a similar fashion.

Nursing staff at the University of Colorado's Outpatient Infusion Center will be responsible for classifying the severity of an IRR for each patient at the end of every ocrelizumab and rituximab infusion using the scale below. Nursing staff will be asked to record the highest grade of an IRR that they observed or intervened upon for each patient after completion of their infusion.

Severity of IRR:

Grade 0: No infusion reaction

Grade 1: Mild reaction (transient flushing or rash drug fever < 38 degrees C); infusion interruption not indicated; intervention not indicated

Grade 2: Requires therapy or infusion interruption but responds promptly to symptomatic treatment (e.g., antihistamines, NSAIDs, narcotics); prophylactic medications indicated for 24 hours.

Grade 3: Prolonged (i.e., not rapidly responsive to symptomatic medication and/or brief interruption of infusion); recurrence of symptoms following initial improvement; hospitalization indicated for other clinical sequelae (e.g., renal impairment, pulmonary infiltrates)

Grade 4: Life threatening consequences; urgent intervention indicated.

Grade 5: Death

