4.5.1 Assessments during Treatment

The following evaluations will be conducted during and post treatment:

Study Visits and Procedures Summary:

Study visits for the switching group include a) screening visit, b) first infusion of 300 mg of ocrelizumab (day 1 or T₀), c) 300 mg of ocrelizumab infusion on day 15 (T₁), d) 600 mg of ocrelizumab at 6 months (+/- 2 weeks) after day 1 (T₂) and, e) a research termination visit between month 12 and 18 - (+/- 2 weeks)(T₃). In some cases, screening procedures may be performed on the first infusion day rather than as a separate visit. The patient may continue on 600 mg of ocrelizumab or (if the patient prefers) 500mg rituximab at T₃, or 12 to 18 months after Day 1 (T₀). A month is defined as 28 days. Study visits for the comparator group include only standard of care infusion of rituximab, up to two infusions per patient, approximately 6 months apart. Research data on IRRs for the comparator group will be collected from the medical records.

A summary of all procedures for switching group is outlined under “Schedule of Events” in **Table 1** below. During the screening visit, patients will be consented for the study and receive both a medical and full neurological exam. Verification of their hepatitis B and C status including testing will be conducted if a patient has not been tested in the last two years. MS disease history and demographic information will also be collected. Patients will also receive an EDSS exam and take an online version of the PDDS (done as standard of care- on an iPad).

The Expanded Disability Status Scale (EDSS) is a commonly used assessment that allows clinicians to objectively measure changes in the disability status of MS patients using unbiased clinical raters.⁷ The **EDSS** provides a total score on a scale that ranges from 0 to 10. The first levels 1.0 to 4.5 refer to people with a high degree of ambulatory ability and the subsequent levels 5.0 to 9.5 refer to the loss of ambulatory ability. The range of main categories include (0) = *normal neurologic exam*; to (5) = *ambulatory without aid or rest for 200 meters; disability severe enough to impair full daily activities*; to (10) = *death due to MS*. In addition, it also provides seven subscale measurements called Functional System (FS) scores.

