The Patient-Determined Disease Steps (PDDS) is a PRO version of the clinician-reported EDSS which hones the stages of cane use and thus is more responsive to mid-range disability changes.⁸ This tool asks the patient to characterize level of disability into one of nine steps (0=normal, 1=mild disability, 2=moderate disability, 3=gait disability, 4=early cane, 5=late cane, 6=bilateral support, 7=wheelchair scooter, 8=bedridden). The PDDS will be used to characterize (and to control for) disability in both study groups at all study time points.

Following the screening visit, patients in the switching group will be scheduled for their first infusion of ocrelizumab at their next regularly scheduled infusion date (no more than six months after their last rituximab infusion). Study infusion cycle T₁ will have an acceptable window of +/- 4 days since it is given 15 days apart, while infusion cycles T₂ and T₃ will have an acceptable window of +/- 14 days since it is administered 6 months later.

Prior to the start of the infusion, blood samples will be collected that will be utilized for several purposes. At infusion cycle time points, T₀, T₂ and T₃ blood samples for the following assessments will be drawn. First, patients will be

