4.9.4 Safety Analysis

The default analysis will be available case for all eligible participants on an intent to treat basis. Alpha = 0.05 for all tests. As in the OPERA I and II randomized clinical trials, the primary and secondary end points will be descriptively presented. Frequencies and percentages for the severity of IRR grades (Grades 0-5) will be presented for both study groups following each infusion time point and overall between groups. 95% confidence intervals for the proportions will be calculated. Differences in the distribution of IRR severity grades between independent samples (i.e. comparison between groups at a common time point) will be tested with the chi-square or Fisher's exact association test, and additionally with ordinal or multinomial logistic regression. If sample sizes are small among some levels of IRR severity grades, they may be collapsed or dichotomized (i.e. Grade 3 or higher, any reaction or no reaction, severe reaction or none as examples) and methods described for binary outcomes under secondary endpoints will be utilized. Dichotomization may be used to make analysis and presentation of results more manageable as well.

The primary endpoint will be the proportion of whether any IRR occurred (yes or no) per infusion cycle per patient in each study group. The secondary endpoints include the proportion per infusion per patient of severe infusion reaction (grade 3 or greater), the proportion of infusion reactions and severe infusion reaction per patient across all infusions, the proportion patients with anti-drug antibodies, and the proportion of patients with depleted B cells. The primary outcome, binary occurrence of IRR per infusion per patient, could be analyzed with logistic or relative risk models, with GEE (generalized estimating equations) and/or GLMM

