4.9.6 Determination of Sample Size

The sample size will be a convenience sample. It is anticipated a minimum of 100 patients will qualify for each cohort (200 total) resulting in studying 300 infusions with ocrelizumab and 200 infusions with rituximab. This is an observational study not designed to demonstrate superiority of ocrelizumab over rituximab in efficacy but instead indicate the magnitude of the relative tolerability and immunogenicity. The primary endpoint is the difference in the percentage of IRRs between the two study groups. In addition, both study groups will include treatment experienced patients on rituximab who have experienced a minimum of two infusions and either continue to stay on rituximab or switch to ocrelizumab.

To estimate study power with the proposed sample size of 100 infusions in each group, we conducted a chart review of 50 patients at the Rocky Mountain MS Center who are currently taking rituximab and examined their IRRs using the proposed IRR grading scale (see section 3.3.1) from Grade 0-5. The number and severity of IRRs were captured following their third rituximab infusion. The highest grade of an IRR that occurred during the infusion was recorded. Our pilot data revealed that following the third rituximab infusion, 14.3% of patients had an IRR of which 85.71% were Grade 0, 12.24% were grade 2 and 2.05% were Grade 3. Hauser et al., found that following the second infusion of rituximab in patients, the majority of whom (60%) were not taking a DMT for 6 months prior to initiating rituximab only 20.3% experienced in an IRR.³

Using IRR estimates from our pilot data and establishing a clinically meaningful difference of 20% increase in IRRs, we conducted the following power analysis for a sample of 95 patients (assuming a 5% attrition rate after recruiting 100 patients in each study group). An IRR proportion for ocrelizumab users at 34.3% compared with 14.3% for rituximab (obtained from our pilot data) for a two sided (alpha = 0.05) two sample proportion test for the null hypothesis of no difference between rituximab and ocrelizumab in proportion of IRRs would result in 90% power for 95 patients per group.

In response to the FDA IND letter, “the power analysis in Section 4.9.6 of the protocol appears to compare the infusion-related reaction (IRR) rate at the third rituximab infusion (14.3%) to that of the first infusion of OCR (34.3%). Because

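### The primary endpoint pools unlike ocrelizumab infusions (Day 1, Day 15, month 6), while the power statement rests on the first ocrelizumab infusion alone

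*Combined protocol and SAP*

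**What the plan says.** Section 3.3.1 defines the endpoint at infusion level: "The primary end point will be proportion of infusions with ≥ 1 IRR between the switching and comparator groups". Section 4.9.4 words it slightly differently: "The primary endpoint will be the proportion of whether any IRR occurred (yes or no) per infusion cycle per patient in each study group".

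The infusions that enter differ by group. For switchers, section 3.1 states that "the first dose of ocrelizumab will be a split dose of 300 mg on day 1 and day 15 followed by 600 mg, six months" (that is, at month 6). For the comparator, section 4.5.1 states: "Study visits for the comparator group include only standard of care infusion of rituximab, up to two infusions per patient, approximately 6 months apart". Section 4.9.6 expects 100 patients per cohort, "resulting in studying 300 infusions with ocrelizumab and 200 infusions with rituximab", which is three per switcher and two per comparator patient.

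The Introduction reports ocrelizumab reaction rates by infusion: "The rate of IRRs was highest during the first infusion or Dose 1 (27.5% on Day 1; 4.71% on Day 15 of Dose 1"), then 13.7% at Dose 2.

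The power calculation in 4.9.6 compares 34.3% with 14.3% in 95 patients per group. In answering the FDA comment, the same section explains this as the first study infusion of ocrelizumab set against a rituximab infusion that is at least the third.

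**The concern.** The question behind the study is whether moving from rituximab to ocrelizumab brings more infusion reactions than staying on rituximab. The infusion that speaks most directly to this is the first ocrelizumab infusion (T0), and it is the one on which the sponsor justifies the sample size. The primary endpoint instead averages T0 with two other kinds of infusion. One of them, Day 15, comes about two weeks after the previous infusion and matches nothing planned in the comparator group.

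If reactions cluster at T0, the average can sit close to the rituximab rate even when T0 does not. A null primary result could then be read as good tolerability of switching, and the stated 90% power would not describe the test that produced it.

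**Working it through.** **Inputs.** Ocrelizumab rates 27.5% (Day 1), 4.71% (Day 15) and 13.7% (Dose 2, taken as month 6) are from the Introduction. The rituximab rate of 14.3%, the planned 34.3%, 95 per group, two-sided alpha of 0.05, 90% power, and 300 v 200 infusions are from 4.9.6.

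**Formula.** With d = p1 − p2 and p̄ the weighted mean rate, SE0 = √[p̄(1 − p̄)(1/n1 + 1/n2)] and SE1 = √[p1(1 − p1)/n1 + p2(1 − p2)/n2]. Power = Φ[(d − 1.96·SE0)/SE1] + Φ[(−d − 1.96·SE0)/SE1]. Infusions are treated as independent because the plan gives no within-patient correlation.

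**1. The plan's own figure.** 34.3% v 14.3%, 95 per group: p̄ = 0.243, SE0 = 0.0622, SE1 = 0.0605. (0.200 − 0.122)/0.0605 = 1.29, so power is 90.1%. The stated 90% is reproduced, for one infusion per patient.

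**2. OPERA rates against 14.3%.**

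| Ocrelizumab infusions used | Rate | Difference | Approximate power |
|---|---|---|---|
| T0 only | 27.5% | +13.2 | 63% (100 v 100), 77% (100 v 200) |
| T0 and month 6 | (27.5 + 13.7)/2 = 20.6% | +6.3 | 38% (200 v 200) |
| All three, as planned | (27.5 + 4.71 + 13.7)/3 = 15.3% | +1.0 | 6% (300 v 200) |

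In this order, month 6 removes 13.2 − 6.3 = 6.9 of the 12.2 points lost, and Day 15 removes 6.3 − 1.0 = 5.3. The split depends on the order: T0 with Day 15 alone gives (27.5 + 4.71)/2 = 16.1%, or +1.8. The mechanism shows in the three separate differences from 14.3%: +13.2 at T0, −9.6 at Day 15 and −0.6 at month 6, with mean +1.0. Day 15 offsets the excess; month 6 adds weight with almost no difference.

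**3. Day 1 at the planned 34.3%, other rates unchanged.**

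- All three: (34.3 + 4.71 + 13.7)/3 = 17.6%, a difference of +3.3. With 300 v 200, p̄ = 0.163, SE0 = 0.0337, SE1 = 0.0331, and (0.033 − 0.066)/0.0331 is about −1.0. Power is about 16%.
- T0 and month 6: (34.3 + 13.7)/2 = 24.0%, +9.7, power about 70% (200 v 200).
- T0 only: +20.0, power about 92% (100 v 100).

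**4. Sensitivity.**

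- Comparator rate from 10% (assumed) to 20.3% (the second-infusion rituximab figure cited in 4.9.6): the pooled difference runs from +5.3 to −5.0, while the T0 difference runs from +17.5 to +7.2.
- Day 15 as high as the comparator: (27.5 + 14.3 + 13.7)/3 = 18.5%, or +4.2.
- Day 1 and Day 15 merged as one dose: the rate for that dose lies between 27.5% and 27.5 + 4.71 = 32.2%. Averaged with 13.7%, this gives 20.6% to 23.0%, or +6.3 to +8.7.

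**The case against.** The strongest reply is that the T0 result is already planned. The primary objective in 2.1 calls for comparison with the comparator at each infusion cycle. Section 3.3.1 lists a count comparison after each infusion, a patient-level comparison, and a within-switcher comparison of Day 1 with the later infusions. Section 4.9.4 tabulates grades by time point with confidence intervals and between-group tests. A clear T0 excess would therefore be visible. This stands, and it limits the point to the primary result. None of these is the primary comparison, though: the count comparison uses rituximab infusions described only as similar, and the Day 1 comparison in 3.3.1 stays within the switching group.

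The second reply is that the OPERA pattern may not apply. About 73% of the ocrelizumab patients in each OPERA trial were treatment-naive, whereas every switcher has had at least two rituximab infusions. The Introduction also raises cytokine release from CD20-expressing cells as a possible cause, in which case already depleted patients might show a flatter profile and little dilution. This also stands. The sizes above are illustrations.

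Third, infusion cycle in 4.9.4 might mean a dose, with Day 1 and Day 15 merged. Section 4.5.1 points the other way ("Study infusion cycle T₁ will have an acceptable window of +/- 4 days since it is given 15 days apart"), as does the count of 300. But 4.5.1 also applies the term to T3, where Table 1 schedules no ocrelizumab administration. The usage is loose enough to need a definition.

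Finally, Day 15 is part of the ocrelizumab schedule in this study, so an all-infusion proportion is a legitimate summary of tolerability. That supports keeping it, though not as the contrast on which the power rests. The mixed and marginal models named in 4.9.4 are there for within-patient correlation; no infusion-number term is specified.

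**Conclusion.** The point holds as a mismatch between the primary endpoint and the contrast used to power it. The endpoint pools three unlike ocrelizumab infusions, and the 90% applies to one. If the OPERA pattern carried over, a 13.2-point excess at T0 would appear as about 1 point in the primary result. With T0 at the planned 34.3%, it would appear as 3.3 points, with power of about 16%. Positive within-patient correlation would tend to lower that further. These figures assume the OPERA rates, a 14.3% comparator rate and equal numbers at each infusion.

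A reader might infer more than the documents support:

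- *That Day 15 alone is responsible.* Dropping only Day 15 still leaves 6.3 of 13.2 points. Nor does its dose set it apart, since Day 1 is also 300 mg; its short interval, low OPERA rate and lack of a counterpart do.
- *That the endpoint is certain to be biased towards no difference.* That depends on the reaction profile in rituximab-experienced patients, which the documents do not give. At a comparator rate of 20.3% the pooled difference turns negative.
- *That T0 and month 6 match the rituximab infusions in spacing.* Six months is the plan, but 4.3.1 says patients are often out of window and accepts intervals of up to 12 months.

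**What to change.** In 3.3.1 and 4.9.4, prespecify the between-group contrast at the first ocrelizumab infusion (T0) as the primary comparison. It can be tested directly or taken from the GEE/GLMM with an infusion-number term that lets T0, Day 15 and month 6 differ. State which rituximab infusions form the reference. Report month 6 against rituximab separately, report Day 15 within the switching group only, and keep the all-infusion proportion as a supportive result.

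Define infusion cycle in 4.9.4 as either each infusion or each dose. Restate the power in 4.9.6 for the contrast actually used, including the case where T0 is nearer 27.5% than 34.3% (about 63% to 77% above).

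The cost is wording and a revised power statement, using data already scheduled for collection. The downside is that about 100 ocrelizumab infusions, instead of 300, enter the primary contrast. A primary comparison on T0 and month 6 together would keep more infusions but would still roughly halve the T0 excess under the OPERA rates.

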3. STUDY DESIGN

3.1 Description of the Study

This is a prospective *between and within group* observational study to determine differences in tolerability, immunogenicity and safety related outcomes for MS patients who have been administered at least two infusions of rituximab, with the last dose of rituximab within 12 months of screening and are willing to be switched to ocrelizumab, compared to patients who are continuing on rituximab as a comparison cohort from the clinic population treated as part of routine clinical care in our program.

The comparator arm is an observational arm only. In addition to prospective data collection, we will collect infusion-related reaction data retrospectively for infusions done after August 1, 2016 (when we began collecting infusion reactions in a standardized way as part of standard of care at the infusion center).

Retrospective data will be collected only after consent is obtained.

In a prospective evaluation with patients at RMMSC who are currently on sustained rituximab treatment for their MS, we will examine the frequency and

severity of IRRs for 100 patients who switch to ocrelizumab (**switching group**) compared to 200 patients continuing rituximab as our primary outcome (**comparator group**). Our secondary outcome is to examine anti-drug antibody formation post switching from rituximab to ocrelizumab (**switching group**). Comparisons for the both outcomes will also be made to findings from the OPERA I and II randomized clinical trials. Other exploratory outcomes including the measurement of B cell reconstitution, cytokine reactions and adverse event profiles will also be examined.

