4. MATERIALS AND METHODS

4.1 Subjects

We plan to enroll 100 patients in the switching group and between 100 and 200 patients in the comparator group (to study 200 infusions) for a total of up to 200-300 patients which would provide adequate power (90%) for the study. To account for screen failures and withdrawals, we are seeking to enroll an additional 50 patients for a total of 250-350 patients. Patients are not confined to only one of the 2 groups. For example, data may be collected from a patient as part of the rituximab arm and then at a later point the patient decides to switch to ocrelizumab. This patient could then be consented into the switching group. Enrollment will occur over a 3-month period at RMMSC.. Dropouts in the switching group that occur prior to the 6 month infusion will be replaced. All patients will be included in the analyses (Intent to Treat Analysis).

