4.1.2 Inclusion Criteria

Switching group:

- Current active patient of RMMSC
- 18-65 years
- Diagnosis of relapsing forms of MS
- Completed **≥ two doses** of rituximab with the last dose having been administered:
 - a) within 12 months of screening
 - and
 - b) at least 6 months prior to first planned infusion of study drug
- Are receiving their current infusions of rituximab at the University of Colorado Outpatient Infusion Center
- Have discussed the possibility of switching to ocrelizumab with their MS provider
- Screened for Hepatitis B and C and TB within 2 years of first dose of ocrelizumab
- A negative serum pregnancy test must be available for premenopausal women and for women <12 months after the onset of menopause, unless they have undergone surgical sterilization.
- Women of childbearing potential must agree to use a “highly effective”, hormonal form of contraception or two “effective” forms of non-hormonal contraception. Contraception must continue for the duration of study treatment and for at least three months after the last dose of study treatment
- Are able to complete patient reported outcomes developed as English written scales.
- Must be able and willing to give meaningful, written informed consent prior to participation in the trial, in accordance with local regulatory requirements

Comparator group:

- Current active patient of RMMSC

- 18-65 years
- Diagnosis of relapsing forms of MS
- Completed \geq **two doses** of rituximab with the last dose having been administered within 12 months of screening as standard of care
- Are receiving their current infusions of rituximab as standard of care at the University of Colorado Outpatient Infusion Center and will continue to do so
- Are willing to be followed for subsequent rituximab infusions during the study period as standard of care, and/or allow retrospective data collection on previous rituximab infusions
- Must be able and willing to give meaningful, written informed consent prior to participation in the trial, in accordance with local regulatory requirements

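### Secondary IRR assessment b sets any reaction over three ocrelizumab infusions against any reaction over a planned mean of one to two rituximab infusions, so equal per-infusion risk appears as an ocrelizumab excess.

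*Combined protocol and SAP*

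**What the plan says.** Section 3.3.1 lists, as secondary IRR assessment b, the between-group difference in the proportion of patients with at least one "IRR across any of their infusions between the switching and comparator groups". Section 4.9.4 has a related secondary endpoint, "the proportion of infusion reactions and severe infusion reaction per patient across all infusions".

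The numbers of infusions differ by design:

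- **Switchers.** IRRs are recorded at three ocrelizumab infusions: day 1 (T0), day 15 (T1) and month 6 (T2) (Section 4.5.1 and Table 1).
- **Comparators.** Section 4.1 plans "between 100 and 200 patients in the comparator group (to study 200 infusions"). Section 4.5.1 allows "up to two infusions per patient, approximately 6 months apart".
- **Totals.** With at least 100 patients per cohort, Section 4.9.6 expects enrolment "resulting in studying 300 infusions with ocrelizumab and 200 infusions with rituximab".
- **Retrospective data.** Section 3.1 adds that "we will collect infusion-related reaction data retrospectively for infusions done after August 1, 2016", and the comparator inclusion criteria let patients join for later infusions "and/or allow retrospective data collection on previous rituximab infusions". No per-patient limit is given for these.

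Section 4.9.4 sets alpha at 0.05 for all tests and has secondary endpoints tested univariately.

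**The concern.** A patient observed at three infusions has more chances to react than a patient observed at one or two. Unless all of a patient's infusions have the same outcome, the proportion with any reaction grows with the number observed. Assessment b therefore mixes the effect of the drug with the number of infusions.

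The methods in Section 4.9.4 do not remove this. GEE and GLMM deal with repeated per-infusion outcomes, whereas assessment b has one value per patient. The exposure terms are optional and belong to models for rates and counts. Matching and propensity methods balance patient characteristics, not infusion numbers. The caveat in Section 4.2 concerns how events are collected.

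At stake is a secondary test whose error rate exceeds 5%, in a study that Section 1 says should show that switching does not bring unexpected infusion reactions. If the Section 4.9.4 wording on severe reactions means a patient-level any-event proportion, that endpoint has the same problem.

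**Working it through.** **The plan's own figure.** Section 4.9.6 gives 90% power for 34.3% v 14.3%, 95 per group, two-sided alpha 0.05. With mean proportion 0.243:

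z = (0.200 × √95 − 1.96 × √(2 × 0.243 × 0.757)) / √(0.343 × 0.657 + 0.143 × 0.857) = (1.949 − 1.189) / 0.590 = 1.29, so power is 90.1%.

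The stated figure is correct on its own inputs and is not in dispute.

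**Inputs for assessment b**
- Risk per infusion p = 14.3% in both groups (pilot, third rituximab infusion, Section 4.9.6).
- 100 switchers with three infusions each.
- 200 comparator infusions from 100 patients (two each), 150 patients (50 with two, 100 with one) or 200 patients (one each).
- Day-15 risk: either 14.3%, or 4.71% from the Introduction's trial figures ("27.5% on Day 1; 4.71% on Day 15 of Dose 1"). Those come from another population, so this is an assumption.
- Within-patient correlation is not in the documents. I use independence and an assumed intraclass correlation (ICC) of 0.3.

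**Any-IRR proportions, independence**, from 1 − ∏(1 − risk):
- Switchers, day 15 at 14.3%: 1 − 0.857³ = 37.1%
- Switchers, day 15 at 4.71%: 1 − 0.857² × 0.9529 = 30.0%
- Comparators, two each: 1 − 0.857² = 26.6%
- Comparators, 150 patients: (50 × 26.6% + 100 × 14.3%) / 150 = 18.4%
- Comparators, one each: 14.3%

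**Any-IRR proportions, ICC 0.3.** With equal risks I use a beta-binomial with α = 0.143 × 0.7/0.3 = 0.334 and β = 0.857 × 0.7/0.3 = 2.000. Over two infusions, 1 − 0.857 × (3.000/3.333) = 22.9%. Over three, 1 − 0.771 × (4.000/4.333) = 28.8%. The 150-patient mix is 17.2%. With day 15 at 4.71%, a one-factor Gaussian copula matched to ICC 0.3 between the 14.3% infusions gives switchers 24.2%.

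**False excess for ocrelizumab, and rejection rate** of the two-sided pooled two-proportion z test at 5%, by exact enumeration. Each range runs from day 15 at 4.71% to day 15 at 14.3%.

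| Comparators | Independence | ICC 0.3 |
|---|---|---|
| 100, two infusions each | 3.5 to 10.5 points; 8% to 36% | 1.4 to 5.9 points; 6% to 16% |
| 150, 200 infusions in all | 11.6 to 18.7 points; 57% to 91% | 7.1 to 11.7 points; 28% to 59% |
| 200, one infusion each | 15.7 to 22.8 points; 89% to 99% | 9.9 to 14.5 points; 56% to 84% |

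**Further checks**
- If day 15 keeps the Introduction's ratio to day 1 (14.3 × 4.71/27.5 = 2.45%), switchers have 28.4% under independence. The excesses are 1.8, 10.0 and 14.1 points, with rejection 6%, 46% and 82%.
- If retrospective data gave each comparator four infusions, comparators would have 1 − 0.857⁴ = 46.1% against 37.1%. The bias would reverse, to −9.0 points.
- Severe IRR at the pilot Grade 3 rate of 2.05%, three v two infusions, independence: 6.0% v 4.1%, rejection 9%.

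**Equal numbers of infusions, equal risk of 14.3%**
- T0 v one comparator infusion: rejection 5.1%, 5.2% and 5.1% with 100, 150 and 200 comparators.
- Two v two infusions (100 v 100), independence: 4.9%.

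**The case against.** The strongest reply is that the harm depends on a scenario the plan may not follow. Section 4.9.6 describes three v two infusions, where the excess may be as small as 1.4 points. Because the first ocrelizumab dose is split, three v two could also be read as reaction burden over two dose courses. Section 3.1 names 200 comparators, who at two infusions each would give 400, and uncapped retrospective data could reverse the direction. All of this stands. But the plan does not state the dose-course reading, and that reading does not cover comparators with one infusion, whom Section 4.1 allows. Uncertainty about the count is itself a reason to fix it in advance.

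Section 4.9.4 also says that endpoints will be presented descriptively, so a test of assessment b is an inference. The same section sets alpha for all tests and has secondary endpoints tested, so testing is the natural reading. The Section 4.9.4 per-patient wording might mean reactions divided by infusions, which would already be normalised. For that endpoint the point is conditional.

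Three objections to the remedy stand in part:
- T0 v one comparator infusion overlaps with the common-time-point comparisons already in Section 4.9.4.
- Its power is lower if the day-1 risk is the Introduction's 27.5%: 64%, 73% and 78% v 14.3% with 100, 150 and 200 comparators.
- The error rates and power above treat the groups as independent, whereas patients may enter both groups and comparators are matched.

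None of these removes the bias in assessment b.

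**Conclusion.** The concern holds and should be fixed. On the planned mean of one to two rituximab infusions, assessment b favours rituximab when the per-infusion risks are equal. The size depends mainly on how many comparators contribute one infusion. With one each, it can exceed the plan's own 20-point meaningful difference; with two each, it may be slight.

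The mechanism follows from the infusion counts and needs only that a patient's outcomes are not perfectly correlated. The sizes rest on the 14.3% pilot risk applied to both drugs, the assumed day-15 risk and the assumed correlation. The direction rests on the 200-infusion target and would change if retrospective infusions raised the comparator mean above three.

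The scope is one secondary assessment, plus severe reactions if Section 4.9.4 means a patient-level proportion. The per-infusion primary endpoint is not affected.

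**What to change.** Amend the SAP wording for assessment b:

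1. **Lead comparison.** Test any IRR at T0 v one prespecified comparator infusion, in all patients. State which comparator infusion counts, whether it may be retrospective, and that it is at least the third rituximab infusion, as Section 4.9.6 assumes.
2. **Supporting comparison.** Compare T0 and T2 with two comparator infusions among patients who have both, and report the number excluded. This should not lead, because it conditions on continuing treatment. If half of those reacting at T0 stopped (an assumption), any-IRR over the two infusions would fall from 26.6% to (0.857 × 0.143 + 0.143 × 0.5) / (0.857 + 0.0715) = 20.9% under independence.
3. **Severe IRRs.** Apply the same rule if Section 4.9.4 means a patient-level any-event proportion.
4. **Total IRRs per patient.** If compared between groups, make the number of infusions the exposure term.
5. **All-infusions proportion.** Report it descriptively, including day 15, with infusions per patient by group.

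No visit, sample or procedure changes. Day 15 and some other infusions leave this one contrast but stay in the primary analysis and the descriptive summary. For the plan's 34.3% v 14.3%, the lead comparison has 92%, 96% and 97% power with 100, 150 and 200 comparators.
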